**Table 6. Interpretation of likelihood ratios**

Likelihood ratio Positive	Likelihood ratio negative	Changes in probability of the condition	Results
> 10	< 0.1	Large	Conclusive
5–10	0.1–0.2	Moderate	Moderately useful
2–5	0.2–0.5	Small	Sometimes useful
< 2	> 0.5	Tiny	Rarely useful
1	1	No change at all	Not useful

*(\*)Modified from: The investigation and management of the small-for-gestational-age fetus Royal College Obstetricians and Gynecologists - RCOG Guideline No. 31 November 2002*

2. For the two biomarkers with the highest sensitivity value we will proceed with an assessment in parallel with a mode "OR". Please note that in this study we use biomarkers in parallel in order to improve the overall specificity with respect to the use of every single biomarker. This implies that the purpose of the study is to develop an organizational model capable of identifying those subjects with MCI with the highest risk of converting to Alzheimer's disease (low percentage of false negative). Consider this theoretical example ([http://www.quadernodiepidemiologia.it/epi/screen/tst\\_com.htm](http://www.quadernodiepidemiologia.it/epi/screen/tst_com.htm)) which will be replicated with data captured in this study. Contingency tables can be set up separately for each of the 2 tests to calculate their sensitivity and specificity.

Compared to using a single test, in the case of interpretation «OR» it is less likely to miss a person with MCI converting to Alzheimer's dementia. However, there will be a low percentage of false negative, i.e. of subjects with AD at the end of the study but with biomarker negative at baseline. With this mode we might get an increase in sensitivity at the expense of specificity. In the case of interpretation «AND», it is easier to miss subjects with MCI converting to Alzheimer's disease, but there is a lower probability that a person with MCI is classified as a subject that will convert to Alzheimer's disease. Specificity increases at the expense of sensitivity.

3. Cox logistic regression models will be performed that will help to identify the best pattern of variables for a subject with MCI candidate for conversion to Alzheimer's disease. For each patient included in the study, biographic and clinical information will be collected that will be used to construct multivariate models. In this regard, the months-person observation in the cohort will be calculated for each patient from the baseline visit to the end of the study or to his/her last visit or death.

Finally, in order to identify the combination of biomarkers to be proposed for selection of patients eligible for treatment with the new anti-dementia drugs, it shall be taken into account both costs and availability on the national territory of centres able to propose the diagnostic work-up, along with the level of invasiveness of the test. From a perspective of research in public health, the critical issues shall be carefully considered relating to standardization of analytical procedures for the determination of a biomarker, as documented by numerous reviews of the the Cochrane Collaboration. In this context the following solutions have been identified:

1. evaluation of "markers" shall occur in "expert centres" previously identified and connected through technology platform or receiving the samples stored at -80° C;
2. Training meetings shall be arranged for the panel of "expert centres" assessors in order to harmonize procedures, minimize the inter-rater variability and create a panel of "expert assessors" for each type of marker certifying the results for the individual subjects;
3. all information of the 400 subjects shall be blinded within a database provided by a professional biostatistical company approved by and under the supervision of the CC so that the assessors' panel of the individual exams is totally unaware whether MCI is 'Stable' or 'Converted' during follow-up. Only at the end of the Protocol will

the encrypted archive be opened and the diagnosis of all the NPT follow-up be coupled to each person;

4. all markers shall be arranged in 2 different presentations (each sample of CSF divided into 2 tubes, each image split into 2 sets of images, each EEG divided into 2 lengths of EEG tracing) in order to have 2 labels for each subject which are also blinded. This procedure will ultimately also provide an idea of the repeatability of the method of evaluation on the same sample/profile/path. Obviously, this does not apply to ApoE genotyping. Also in this case the assessors will be blinded to the fact that a particular exam is the second of the pair of an individual patient or the first of another patient;
5. each individual marker shall express a single assessment (altered/not altered) taken unanimously by the assessors. In the case of "altered", a severity level of 2 or 3 of the alteration (A1, A2 ...) will be scored to check at a later time whether they correlate with rapidity of MCI→AD progression and with the possible rapid worsening of the disease. In the event of a discrepancy between the evaluators who have assessed that particular marker (called N), a strategy of consensus will be built among the evaluators in order that the exam be considered in the final statistical evaluation. K statistics shall be used to estimate the degree of agreement between 2 raters.

Statistical analyses shall be performed by using the softwares STATA and SPSS (version 25.0).

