## **2. OBJECTIVES OF THE STUDY**

Whereas scientific literature is always more abundant in contributions to the profiles of individual sensitivity and specificity biomarkers, much fewer studies have evaluated combinations of multiple markers on the same study population. Furthermore, to date no study has assessed and validated an organization model for screening large part of the population using combinations of biomarkers, in terms of feasibility of costs, distribution and operational feasibility. Indeed these are the key points that this Protocol seeks to address.

The primary aim is to identify a biomarker or a set of biomarkers able to predict with greater accuracy the conversion of MCI to Alzheimer's dementia after 2 or 3 years of follow-up. The secondary aim is to define an optimal organizational model, as regards transferability in clinical practice of the defined diagnostic path of the primary objective as well as sustainability costs, in order to identify patients eligible to prescription of antidementia drugs which are currently under experimentation by RCTs.

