### 3.9 Sample size

In order to calculate the sample size of this study which aims at identifying with the greatest possible accuracy the biomarker or set of biomarkers which could predict conversion from MCI to Alzheimer's dementia, the biomarkers are used as screening tests and then for their level of the sensitivity and specificity. The following table shows the sensitivity value pairs of seven biomarkers that were proposed in this study on the basis of evaluation of the literature reported in section 1.2 of the introduction.

**Table 1. Pairs of sensitivity values of seven biomarkers included in the study. The table shows that one pair of biomarkers (in bold and with an asterisk) is the combination of values of the highest sensitivity, including the use of**

DFR (FCSRT) and EEG. These two biomarkers were therefore taken into account for the calculation of sample size. Tables 2 and 3 show the values of sensitivity, specificity and positive/negative predictive value of the two biomarkers.

	MMSE	CSF p-tau	(  F)FDG-PET	DFR (FCSRT)	APOE4	EEG	Volumetric MRI
MMSE							
CSF p-tau	57/71						
(  F)FDG-PET	57/57	71/57					
DFR (FCSRT)	57/81	71/81	57/81				
APOE4	57/52	71/52	57/52	81/52			
EEG	57/87	71/87	57/87	81/87*	52/87		
Volumetric MRI	57/60	71/60	57/60	81/60	52/60		

Table 2 Data included in Grande's paper et al. submitted

Giulia	AD					
follow-up 2.5 anni	1	0				
DFR	1	59	33	92	sens	0.81
	0	14	81	95	spec	0.71
		73	114	187	vpp	0.64
					vpn	0.85

Table 3 Poil's study et al. 2013 (follow-up of 2 year) (EEG)

Poli 2013	AD					
follow-up 2 anni	1	0				
EEG	1	7	8	15	sens	0.88
	0	1	14	15	spec	0.64
		8	22	30	vpp	0.47
					vpn	0.93

In 2 years of the follow-up the conversion rate from MCI to AD is 26.6% (8/30). In summary, after a follow-up of about 2.5 years, the prevalence of AD in a cohort of patients with MCI ranges from 26.6% to 39%. Based on these data, it was decided to adopt 2 approaches, one based on the methodological work of Bujang & Adnan (Requirements for Minimum Sample Size for Sensitivity and Specificity Analysis. J Clin Diagn Res. 2016 Oct; 10 (10): YE01-YE06), the other using the logic of a case control study, in which the cases are represented by patients converting to Alzheimer's disease, while the control is represented by patients with MCI. In the latter case an OR was

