### 3.10 Statistical Analysis

Statistical analysis will be carried out following three areas:

1. Preparation of contingency tables for each of the seven biomarkers (MMSE; FCSRT; CSF CSF tau and p-tau/ABeta; F)FDG-PET; ApoE4; EEG) and processing parameters of sensitivity, specificity, positive predictive value and negative predictive value and overall accuracy. We will also calculate the positive and negative likelihood ratios (LR). The related 95% CI for each of these parameters shall also be calculated. The results will be compared with the positive and negative LR values, which are considered the gold standard for the placing on the market of a diagnostic test. (Jaeschke R, Guyatt GH, Sackett DL 1994)(see below).

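### The pair rule in section 3.10 ranks markers on sensitivity alone and commits to OR, which on the protocol's own figures works against the aim of greatest accuracy

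*Protocol*

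**What the plan says.** - **Aim (section 2):** to "identify a biomarker or a set of biomarkers able to predict with greater accuracy". The primary endpoint in section 3.7 also asks for the marker or set with the higher accuracy.
- **Single markers (section 3.10, item 1):** "Preparation of contingency tables for each of the seven biomarkers", with sensitivity, specificity, predictive values, overall accuracy and likelihood ratios. The list that follows names six markers; volumetric MRI is missing.
- **Pair (section 3.10, item 2):** "For the two biomarkers with the highest sensitivity value we will proceed with an assessment in parallel", in OR mode. A textbook two-test example is given, "which will be replicated with data captured in this study". The AND reading is described, but the pair is committed to OR.
- **Purpose of OR:** the item says "we use biomarkers in parallel in order to improve the overall specificity". Shortly afterwards, also about OR, it says "With this mode we might get an increase in sensitivity at the expense of specificity".
- **Expected pair (section 3.9, Table 1):** "one pair of biomarkers (in bold and with an asterisk) is the combination of values of the highest sensitivity", namely FCSRT and EEG (81/87).
- **Other combinations (section 3.10, item 3):** multivariable models to find the best pattern of variables. The final proposal also weighs cost, availability and invasiveness.

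**The concern.** Choosing on sensitivity alone ignores half of accuracy: a test that is positive in everyone would rank first. Combining the two most sensitive markers by OR then lowers specificity further. It also ignores how the two markers behave together, although that is the reason for studying a pair.

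Section 3.9 says the result should be accurate enough to trigger a decision to prescribe. If the one pair carried forward as a decision rule is less accurate than one of its own members, the main combination result does not serve the aim. A better rule in the same data would not be reported in comparable terms.

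**Working it through.** **Inputs.** Section 1.2, sensitivity / specificity: MMSE 0.57/0.86, FCSRT 0.81/0.71, CSF 0.71/0.77, FDG-PET 0.57/0.67, APOE4 0.52/0.66, EEG 0.87/0.64, volumetric MRI 0.60/0.75. Conversion is 40% (section 3.9).

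**Reproducing the plan's figures.**
- FCSRT, Table 2: 59/73 = 0.81 and 81/114 = 0.71.
- EEG, Table 3: 7/8 = 0.875 (printed as 0.88 there and 0.87 elsewhere) and 14/22 = 0.64.
- First sample-size row: a two-sided exact binomial test with 155 converters gives power 0.818 and p 0.044; 155/0.40 = 387.5, so 388.
- The protocol gives no accuracy figure for any pair.

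**Formulas.** The protocol has no joint data, so independence given outcome is assumed.
- OR: Se = 1 − (1 − Se1)(1 − Se2); Sp = Sp1 × Sp2.
- AND: Se = Se1 × Se2; Sp = 1 − (1 − Sp1)(1 − Sp2).
- Accuracy = 0.4 Se + 0.6 Sp; Youden J = Se + Sp − 1.

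**The pair and mode the rule selects: FCSRT+EEG by OR.**
- Se = 1 − 0.19 × 0.13 = 0.975; Sp = 0.71 × 0.64 = 0.454; J = 0.430.
- Accuracy = 0.4 × 0.9753 + 0.6 × 0.4544 = 0.663.
- LR+ = 0.9753/0.5456 = 1.79; LR− = 0.0247/0.4544 = 0.054.
- PPV = 0.3901/(0.3901 + 0.3274) = 0.54.

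Over all 21 OR pairs this ranks 9th on J and 11th on accuracy. Table 6 puts an LR+ below 2 in its rarely useful band.

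**Comparators.**

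| Rule | Se | Sp | J | Accuracy | LR+ |
|---|---|---|---|---|---|
| FCSRT+EEG, OR (planned) | 0.975 | 0.454 | 0.430 | 0.663 | 1.79 |
| FCSRT alone | 0.81 | 0.71 | 0.52 | 0.750 | 2.79 |
| MMSE+CSF, OR (best OR pair) | 0.875 | 0.662 | 0.538 | 0.747 | 2.59 |
| FCSRT+EEG, AND | 0.705 | 0.896 | 0.600 | 0.819 | 6.75 |
| MMSE+CSF, AND | 0.405 | 0.968 | 0.373 | 0.743 | 12.6 |
| MMSE+FCSRT, AND | 0.462 | 0.959 | 0.421 | 0.760 | 11.4 |

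FCSRT+EEG by AND is best of all 42 pair-and-mode combinations on both J and accuracy. The last two rows are the only combinations with LR+ above 10.

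**Why OR loses to FCSRT alone.** Adding EEG by OR gains 0.4 × 0.19 × 0.87 = 0.066 from rescued converters. It loses 0.6 × 0.71 × 0.36 = 0.153 from new false positives. The net change is −0.087, which is 0.663 − 0.750.

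**Dependence.** A Gaussian copula with the same correlation in converters and non-converters gives:
- Correlation 0.2: planned OR pair, accuracy 0.673 (10th of 21); same pair by AND, 0.809; MMSE+CSF by AND, LR+ 9.2.
- Correlation 0.4: 0.684 (9th), 0.798 and 7.2.

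FCSRT+EEG by AND stays first on accuracy. The LR+ values above 10 do not survive. Under any dependence the OR pair's false-positive rate is at least EEG's 0.36, so its LR+ cannot exceed 1/0.36 = 2.8.

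**Optimism under the current rule.** If markers are re-ranked on study data, simulation with 160 converters (40% of 400) inflates OR sensitivity by 0.02 points at the literature values. With seven equal sensitivities it is 1.2 points (all 0.8) to 2.1 points (all 0.7). With 85 converters (26.6% of 320) the worst of these is 2.8 points. If the pair is fixed from Table 1, this bias is zero.

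**The case against.** The strongest defence is that item 2 also states a goal of few false negatives. On that goal the rule works: the planned pair's LR− of 0.054 is the best of all 42 combinations and below Table 6's 0.1 line. This stands, but few false negatives is not the accuracy that section 2 and the primary endpoint name, and the specificity sentence contradicts it.

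A second defence is that the AND comparison favours the very pair the rule picks. That is true on J and accuracy, but the plan commits the pair to OR. A generous reading of the worked example might also yield AND figures, though only for that pair. The AND pairs with LR+ above 10 miss more than half of converters (sensitivity 0.41 and 0.46), so which pair is better depends on a criterion the protocol does not state.

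A reader might infer more than the documents support:
- **That other pairs are never examined.** Item 3's models may explore them. They do not commit to sensitivity, specificity or likelihood ratios for any other pair.
- **That the reported accuracy is necessarily optimistic.** The text does not settle whether the pair is fixed from Table 1 or re-ranked on study data. The bias is nil in the first case and small in the second.
- **That a missed pair would meet the 90% conversion risk in the synopsis.** None does: the highest PPV of the 42 is 0.893. The 90% is background rationale, not an analysis threshold.
- **That the lack of a validation method is itself an error.** It may lie in a statistical analysis plan that is not shown.

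The missing MRI in item 1's list is editorial, since MRI is one of the seven markers throughout the rest of the protocol.

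**Conclusion.** The concern holds as a mismatch between a stated rule and the stated aim. On the protocol's own values the rule leads to an OR pair with accuracy 0.663. That is 8.7 points below FCSRT alone, 8.5 points below the best OR pair (0.747) and 15.6 points below the same two markers under AND (0.819). The sentence on specificity is wrong as written: specificity falls to 0.454 from 0.71 and 0.64.

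The sizes assume the literature values, 40% conversion and conditional independence. Equal positive correlation of 0.2 to 0.4 narrows the gap to FCSRT alone to between 6.6 and 7.7 points and does not reverse it. A quite different dependence in converters and non-converters could change the ranking. EEG's sensitivity rests on eight converters (interval 0.47 to 1.00), so the study may rank markers differently; the flaw in the rule does not depend on which pair it picks. Selection optimism is a minor part of the point: about 0 to 2 points of OR sensitivity with 160 converters, and only if the markers are re-ranked on study data.

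**What to change.** 1. Replace the top-two-sensitivity rule in item 2 with an assessment of all 21 pairs of the seven markers, volumetric MRI included, under both OR and AND. Add MRI to item 1's list.
2. State in advance one accuracy criterion tied to the aim, and select the pair on it. If few false negatives is also required, write it as an explicit constraint.
3. Correct the sentence that gives improved specificity as the purpose of OR.
4. Report bootstrap-corrected sensitivity, specificity, predictive values and likelihood ratios for the selected pair, repeating the whole selection in each resample. The wider search needs this: in simulation at the literature values, choosing the best of 21 OR pairs inflated Youden J by about 3 to 4 points.

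The cost is some analysis time and slightly lower reported accuracy. All the data are already planned.

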### **3.11 Monitoring of the study**

Some general aspects of the study will be monitored centrally by the P.I. and the CC through CDMS as, for example, evaluation of the conduct of the study, including periodic evaluation of the quality and timely arrival of data, patient recruitment, evaluation of the centres' activities, etc. The monitors shall use the medical records as central documentation. After every visit at the centres, the monitor shall fill in an *ad hoc* form "Summary of monitoring results". This documentation will be evaluated by the CC. During the study each CC will receive 3 monitoring visits by the CC.

### 3.12 Ethical aspects

Once signed the 'informed consent', the MCI candidate will be notified by the CC prior to enrollment for approval. Researchers will establish and maintain ongoing communication with patients, since in the MCI prodromal to AD no caregiver is needed, in line with the autonomy of individuals and with medical confidentiality. Each recruiting centre shall identify a "contact point for the study protocol", adequately trained for the enrolled subjects. The study shall be submitted for approval of the Ethics Committee of the coordinators' centre and of the ethics committees of the participating clinical centres.

### 3.13 Gantt Diagram

The activities of the various phases of the study will be as follows: 6 months for the preparatory activities, recruitment and collection of biomarkers, 42 months for follow-up and data analysis and 6 months for the release of the results. The Gantt chart is shown in figure 2.

Figure 2. The Gantt chart

	M1-6	M7-12 (T0)	M13-18 (T1)	M19-24 (T2)	M25-30 (T3)	M31-36 (T4)	M37-42 (T5)	M42-48 (T6)	M49-54
Identification of the Hubs of the network, harmonization meetings from ECs, preparation of technological platform									
Subjects enrollment									
Neuropsychological testing									
Neurological and Medical exam									
Biomarkers collection (MMSE; FCSRT; CSF p-tau e CSF tau/ABeta ;(  F)FDG-PET;APOE4;EEG, volumetric MRI)									
Neuropsychological tests and functional scales (follow-up)									
Neurological exam (follow-up)									
Results evaluation									

### 3.14 Costs of the study (Euros)

COSTS	Reserved to the Call For Recruiting Centers	Reserved for Expert Centres	General costs	Total
(  F)FDG-PET 400 x 1.000 Euro each	320.000	80.000	-	400.000
Volumetric MRI 400 x 400 Euro each	128.000	32.000	-	160.000
ApoE 400 x 150 Euro each	30.000	30.000	-	60.000
Lumbar Puncture for Beta/Tau metabolites 400 x 300 Euro each	60.000	60.000	-	120.000
Digital EEG recording and connectivity analysis. 400 50 Euro each	10.000	10.000	-	20.000
Neuropsychological battery (400 pz x 7 follow-up evaluations) 2800 70 Euro each	156.000	40.000	-	196.000
Transfer of Patients	280.000	-	-	280.000
Biologic sample shipping	10.000	-	-	10.000
Web master	-	-	20.000	20.000
Development of technological platform for data transfer	-	-	50.000	50.000
Database & Insurance	-	-	294.000	294.000
Study Coordination	-	-	50.000	50.000
Clinical Centres (n=20) (1 FTP each x 4 years)	1.200.000	-	-	1.200.000
Expert Centres (n=4) (1 FTP x 4 years)	-	400.000	-	400.000
Statistics & database management (1 FTP x 4,5 years)	-	-	90.000	90.000
Biorepository	-	-	-	20.000
Meetings for Harmonization (one for each Marker, 2 full days) +	-	-	63.000	63.000

compliance meeting (3 h)				
Other costs	20.000	20.000	20.000	60.000
Total	2.214.000	672.000	587.000	3.473.000

## Annex 2. Neuropsychological tests and rating scales

The neuropsychological assessment includes: a) an assessment of subjective complaints and of the awareness of cognitive modifications by the subject and his/her relatives/close acquaintances; b) a formal assessment of the main cognitive domains; c) a quantitative functional evaluation; d) a global clinical judgement of severity. These four aspects are jointly required to diagnose a MCI condition, which is the entry criteria for the study (subjective complaints, objective cognitive impairment, no relevant functional impairment, no dementia).

a) The importance of a quantitative assessment of subjective complaints in the AD continuum has emerged only recently (see for example the INSIGHT-AD study- Cacciamani et al., 2017). There is a limited choice of tools standardized for the Italian language. We will adapt 2 instruments validated in English:

-Cognitive Function Instrument (CFI; Walsh et al., 2006; an Italian adaptation is under way): 14 questions, given to the subject and to an informant. In a longitudinal study with a 4-year follow-up (Amariglio et al., 2015), the combination of CFI and CDR was highly predictive of cognitive impairment progression .

-Healthy Aging Brain Care Monitor (HABC-M; Monahan et al., 2012; 2014), assessing how frequently the subject has met difficulties in daily life during the last 2 weeks, as judged by the subject and by an informant. The difficulties may involve 3 macro-domains: cognitive (6 questions), functional (11 questions) and psycho-behavioural (10 questions).

b) Besides the screening test (MMSE), the neuropsychological battery includes the following tests:

### Memory:

The assessment of episodic memory is required as a core criterion for the diagnosis of a typical presentation of AD:

-Free and Cued Selective reminding according to the Italian version (Frasson et al. 2011; Clerici et al. 2017): it is an episodic memory test controlling for encoding of information and for the effectiveness of cueing during retrieval, following the recommendations of the IWG.

-Episodic Memory Score (Marra et al., 2016), a composite measure based on the score of Rey's wordlist learning test (Gainotti et al., 2001) and the delayed recall of Rey's figure (Caffarra et al., 2002).

